### 6.3. Other Endpoints

#### 6.3.1. Demographic, Medical History, and Baseline Characteristics

Disposition variables will include enrolled, randomized, vaccinated, completed, and discontinued. Discontinuations will be split into reasons for discontinuation.

The demographic characteristics will include sex, race, racial designation (completed only if race = Asian), ethnicity, and age on the day of vaccination. Age on the day of vaccination will be derived in years ( $[\text{vaccination date} - \text{date of birth} + 1]/365.25$ ) and truncated to 0 decimal places. For subjects randomized but not vaccinated, the randomization date will be used instead of the vaccination date in the calculation of age.

Colonization status at baseline (Visit 1 or/and Visit 2 admission sample) will be compiled separately for each anatomical site (nose and throat), as well as “any anatomical site” (meaning both sites combined). The definition of colonization status when combining sites is described in [Section 8.1.4](#).

Body mass index (BMI), vital signs, colonization status at baseline, smoking status, alcohol consumption, and elapsed days from vaccination to index surgery will be summarized.

- BMI will be calculated as (weight [kg]/height [m] squared) and rounded to 1 decimal place.
- Vital signs include temperature (°C or °F), blood pressure (systolic and diastolic), pulse rate, and respiratory rate. All temperatures will be converted to °C.
- Alcohol consumption will be recorded as yes/no. If “yes,” then the number of units per week will be recorded.
- Elapsed days from vaccination to the index surgery will be the date of the index surgery minus the date of vaccination, plus 1.

Medical history data will be categorized according to the Medical Dictionary for Regulatory Activities (MedDRA) and summarized by vaccine group.

The Charlson Comorbidity Index (CCI) is a validated prognostic indicator for which factors, individually or in combination, may increase the risk of short-term mortality for subjects enrolled in longitudinal studies. On completion of the physical examination at Visit 1, the investigator will record the presence of each comorbid condition and age cohort as presented in [Table 5](#). The sum of the values for each comorbid condition is added to the subject’s value for age to obtain the CCI score. The 10-year mortality probability is calculated as  $0.983^{\text{EXP}[0.9 \times \text{CCI score}]}$  (Kastner et al).

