#### **6.3.4. Colonization with *Staphylococcus aureus***

If 2 or more samples associated with postsurgery are obtained, only the colonization results from the latest visit will be eligible for analysis.

Four colonization endpoints, based on colonization results from scheduled visits, are specified:

1. The number and proportion of subjects in each vaccine group determined to be colonized with *S aureus* on each scheduled visit where swab samples are collected. Colonization at each visit will be compiled separately for each anatomical site, and for any anatomical site. A subject will be considered positive for “any anatomical site” if either site, or both, is positive.
2. Subject carriage status will be characterized across visits as persistent, indeterminate, intermittent, or noncarrier. Characterizations will be performed by anatomical site and any anatomical site. Characterizations will be based on number of visits where colonization results were obtained, limited to Visits 1, 2 (both the day of surgery and the day of discharge), 4 (Day 42), 5 (Day 90), and 6 (Day 180). Rules for determining carriage status are described next and are also illustrated in [Table 7](#).
  - Persistent: positive at 4 of 5, 5 of 5, 5 of 6, or 6 of 6 visits.
  - Indeterminate: exactly 3 or 4 visits, regardless of combination of positive/negative results.
  - Intermittent: positive at 1 or 2 visits if 2 visits are available, positive at 1 to 3 visits if 5 visits are available, positive at 1 to 4 visits if 6 visits are available.
  - Noncarrier: no positive results at any visit, minimum of 5 visits.

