**Table 7. Rules for Determining Carriage Status**

No. Positive Results							
No. Visits Available	0	1	2	3	4	5	6
1	Missing	Missing	N/A	N/A	N/A	N/A	N/A
2	Missing	Intermittent	Intermittent	N/A	N/A	N/A	N/A
3	Indeterminate	Indeterminate	Indeterminate	Indeterminate	N/A	N/A	N/A
4	Indeterminate	Indeterminate	Indeterminate	Indeterminate	Indeterminate	N/A	N/A
5	Noncarrier	Intermittent	Intermittent	Intermittent	Persistent	Persistent	N/A
6	Noncarrier	Intermittent	Intermittent	Intermittent	Intermittent	Persistent	Persistent

Abbreviation: N/A = not applicable.

3. Acquisition is defined as a positive swab at any postsurgery visit, given that the results for the vaccination and presurgery visits were both negative. The proportions of acquisitions will be compiled for each subsequent postsurgery visit and “any postsurgery visit.” The denominator at each visit will be the number of subjects with at least 1 nonmissing swab result. Acquisition will be compiled for nose, throat, and “any anatomical site.”
4. Clearance is defined as 2 consecutive postbaseline negative swabs, given that all preceding swabs were positive. The proportions of clearances will be compiled for each postbaseline visit. The denominator at each visit will be the number of subjects with at least 1 nonmissing swab result. The analyses will be performed for nose, throat, and “any anatomical site.”

Colonization, carriage status, acquisition, and clearance will be compiled for “any *S aureus*,” MRSA, and methicillin-sensitive *S aureus* (MSSA).

Capsule type will be identified for each *S aureus* isolate as either CP5 or CP8. A small subset of isolates will be neither capsule type, so these isolates will be considered missing for capsule type. Carriage status, acquisition, and clearance will be obtained for each capsule type. These endpoints will be identified as capsule-type persistence, capsule-type intermittent, capsule-type noncarrier, capsule-type acquisition, and capsule-type clearance. Analyses with these endpoints may be performed.

Other endpoints based on clonal complex (CC) and sequence type (ST) may be explored. *S aureus* protein A (*Spa*) typing and capsule typing may be examined only for PDIs with microbiologically confirmed *S aureus* infection.

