Colonization results obtained after a culture-confirmed efficacy endpoint will not be included in deriving characterizations or acquisition. Results from unscheduled visits will not be included in characterizations for persistence, intermittent, etc.

Statistical methodology for colonization is described in [Section 8.1.3.4](#).

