#### **8.1.3.4. Colonization with *Staphylococcus aureus***

Colonization values obtained up to 7 days before vaccination until the day of admission for surgery will be considered eligible baseline values.

Colonization at each visit, acquisition, and clearance are binary endpoints, so they will be summarized with proportions. Vaccine groups will be compared using the CMH test. Site will be the stratification variable.

Carriage status will form a  $3 \times 2$  table with 3 categories—“persistent,” “intermittent,” and “noncarrier”—and 2 vaccine groups. “Indeterminate” will be considered a missing value. Vaccine groups will be compared using the CMH test. Site will be the stratification variable.

Subgroup analyses will be performed by executing logistic regressions with the dependent variable of the proportion of subjects colonized. The model terms will be vaccine group, subgroup, and vaccine group–subgroup interaction. The colonization results for subgroups with significant interactions, defined as  $p < 0.10$ , will be examined more closely.

One subgroup will be examined at a time. Anatomical sites will be examined separately. Only colonization at scheduled visits will be included. Only *S aureus* colonization will be analyzed because the purpose is to see if vaccine group has different effects within subgroup levels.

Vaccine groups will be compared using the Fisher exact test, 2-sided, for the proportion positive for *S aureus* from unscheduled visits. Stratification by clinical site is not proposed because the unscheduled visits will presumably be associated with possible BSI/SSI/ISA.

The number of these assessments per site should be low. Analyses will be performed by anatomical site and for anatomical sites combined.

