**8.2.3.4. Colonization with *Staphylococcus aureus***

All analyses will be performed using the mITT colonization population.

The proportions of subjects with positive swabs will be plotted against time point. The time points' labels on the figures will be "Day of Vaccination," "Day of Surgery," "Day of Discharge," "Day 42," "Day 90," and "Day 180." The values for the time points will be -15, 1, 2, 42, 80, and 180. The legend will identify anatomical site (nasal/oropharyngeal/combined). Plots will be created for "any *S aureus*," MSSA, and MRSA.

Subgroup analyses will be performed on colonization, carriage status, acquisition, and clearance. The subgroups will be age group, sex, baseline colonization status, and primary endpoint (case or noncase). The subgroup analysis of the primary endpoint will be limited to scheduled visits within 90 days, as per definition of the primary endpoint.

A further subgroup will be defined by subjects having any decolonization measures or preadmission antimicrobial agent(s) before surgery (response = yes/no). These analyses will be performed only for "any *S aureus*."

The analysis of matching isolates from microbiologically confirmed cases will be performed separately for nose and throat for each of the efficacy endpoints (BSI and/or deep incisional or organ/space SSI within 90 days, BSI and/or deep incisional or organ/space SSI within 180 days, SSI within 90 days, SSI within 180 days, ISA disease within 90 days, and ISA disease within 180 days), but limited to subjects in the mITT colonization population. If there may be more than 48 cases for the primary endpoint, ie, with BSI and/or deep incisional or organ/space SSI, these extra cases will be included in this analysis.

Colonization analyses and their statistical tests are summarized in Table 25.

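### Swabs taken after a confirmed S aureus infection are dropped from carriage status and acquisition but still count towards clearance, so infected carriers who later test negative are scored as cleared

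*SAP*

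**What the plan says.** SAP Section 6.3.4 defines four colonization endpoints from scheduled swabs: colonization at each visit, carriage status, acquisition and clearance.

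- **Carriage status:** "Subject carriage status will be characterized across visits as persistent, indeterminate, intermittent, or noncarrier".
- **Acquisition:** "Acquisition is defined as a positive swab at any postsurgery visit, given that the results for the vaccination and presurgery visits were both negative".
- **Clearance:** "Clearance is defined as 2 consecutive postbaseline negative swabs, given that all preceding swabs were positive". It is compiled at each postbaseline visit, over everyone with a swab result.

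After Table 7 the section sets the rule at issue: "Colonization results obtained after a culture-confirmed efficacy endpoint will not be included in deriving characterizations or acquisition". The next sentence reads: "Results from unscheduled visits will not be included in characterizations for persistence, intermittent, etc".

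On baseline, Section 8.1.3.4 says: "Colonization values obtained up to 7 days before vaccination until the day of admission for surgery will be considered eligible baseline values". Section 6.3.1 agrees: "Colonization status at baseline (Visit 1 or/and Visit 2 admission sample) will be compiled separately for each anatomical site". The first postbaseline swab is therefore the discharge swab.

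Section 8.2.3.4 says: "Subgroup analyses will be performed on colonization, carriage status, acquisition, and clearance". Primary-endpoint status (case or noncase) is one of the subgroups, limited to scheduled visits within 90 days. Table 25 gives the purpose of the clearance endpoint as exploring whether vaccination helps subjects clear S aureus.

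**The concern.** The SAP treats swabs taken after a confirmed infection as unfit for two of its derived endpoints, then accepts them for a third without giving a reason. Clearance is the endpoint most exposed, because anything done about the infection is likely to push later swabs negative, and negative swabs are what clearance counts.

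At stake is mainly the case/noncase clearance table. It could show infected subjects clearing carriage more often than uninfected ones because of the derivation rule, and a reader could take that for biology.

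**Working it through.** The documents give no figure for clearance, so there is nothing to reproduce. The check applies the written rules.

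**1. Does the exclusion reach clearance?** Section 6.3.4 uses the verb characterize for carriage status only, and the sentence after the exclusion ties characterizations to persistence and intermittent carriage. Acquisition has to be named separately, so characterizations is not a general term for derived endpoints. Nothing in Sections 8.1.3.4 or 8.2.3.4 or in Table 25 extends the exclusion.

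**2. Which swab patterns score as clearance?** There are six scheduled swabs (Visit 1, admission, discharge, Days 42, 90 and 180), giving 2^6 = 64 complete patterns. With Visit 1 and admission as baseline, both must be positive. Clearance is then scored for:

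- discharge and Day 42 negative, Days 90 and 180 free: 4 patterns;
- discharge positive, Days 42 and 90 negative, Day 180 free: 2 patterns;
- discharge and Day 42 positive, Days 90 and 180 negative: 1 pattern.

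The total is 4 + 2 + 1 = 7 of 64.

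**3. What happens to cases?** With onset between discharge and Day 42, only the discharge swab is both postbaseline and pre-infection. All 7 patterns need Day 42 or a later swab, so every recorded clearance uses at least one post-infection swab. Two examples:

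| Visit 1, admission, discharge, Day 42, Day 90, Day 180 | Onset | As written | Post-infection swabs excluded |
|---|---|---|---|
| + + + - - - | before Day 42 | cleared at Day 90 | not cleared |
| + + + + - - | after Day 42 | cleared at Day 180 | not cleared |

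The case/noncase analysis stops at Day 90. There, a wholly pre-infection pair exists only when discharge and Day 42 are both negative and onset follows the Day 42 swab.

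**4. Size in the pooled result.** Inputs are 48 target cases and about 6,000 enrolled (SAP 2.1), 10% dropout (Protocol 9.2), and 20-50% carriage (the general-population range in Protocol Section 1, assumed to hold for cases). Subjects with swabs: 6,000 x 0.9 = 5,400. If every carrier among the cases were scored as cleared:

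- 20% carriage: 48 x 0.20 / 5,400 = 0.18 percentage points;
- 50% carriage: 48 x 0.50 / 5,400 = 0.44 percentage points;
- all cases carriers: 48 / 5,400 = 0.89 percentage points.

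For the arm difference, take the protocol's final success boundary of 14 against 34 cases, with 2,700 subjects per arm: (34 - 14) x 0.20 / 2,700 = 0.15 and (34 - 14) x 0.50 / 2,700 = 0.37 percentage points. An even split gives zero.

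**5. Size in the case/noncase table (illustration).** None of these inputs is in the documents: carriage loss of 0.3, 0.6 or 1.0% per day, vaccination 30 days before surgery, median onset Day 15, and carriage ended by treatment in 40% or 70% of cases. Simulating Visit 1 carriers with swabs through Day 90 gives:

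| Daily loss | Noncases cleared | Cases, 40% | Cases, 70% |
|---|---|---|---|
| 0.3% | 0.108 | 0.421 | 0.655 |
| 0.6% | 0.186 | 0.439 | 0.628 |
| 1.0% | 0.255 | 0.445 | 0.587 |

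The case-to-noncase ratio runs from 0.445/0.255 = 1.7 to 0.655/0.108 = 6.1. Over 99% of the case clearances rest on a post-onset swab. These are proportions of Visit 1 carriers. The SAP's denominator is all swabbed subjects, so its tabulated proportions would be smaller.

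**The case against.** The strongest reply is that little depends on this. Colonization is exploratory, and Section 8.1.4 treats significant subgroup findings as hypothesis generating. Clearance by case status rests on one sentence in Section 8.2.3.4; the subgroup model in Section 8.1.3.4 and the subgroup row of Table 25 cover only the proportion colonized. Only cases positive on every earlier swab can contribute. All of this stands and limits the weight of the point, but it does not explain why clearance is left out of the exclusion.

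It is also fair that the documents do not say antibiotics cause the later negatives. Protocol Section 6.4.2 only requires the therapy to be recorded. A reader might infer that clearance in cases simply measures treatment. That is plausible but unproven, and the inconsistency does not depend on it.

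A reader might further infer a second error: carriage lost between vaccination and surgery is not scored, because a negative admission swab is a baseline value and breaks the run of positives. The documents do not support calling this an error, for three reasons:

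- It follows the protocol's own baseline (Section 9.3.4.2, Visit 1 and the admission sample). It applies only when the admission swab was taken: with that swab missing, Visit 1 positive followed by discharge and Day 42 negative still qualifies.
- Early loss remains visible by arm, because colonization is compared at each visit, including the day of surgery.
- Starting from Visit 1 alone would count presurgery decolonization (Protocol Appendix 2) as clearance.

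Nor does the model above show as much carriage loss missed as counted. With the Day 180 swab included, loss before admission (0.086, 0.165, 0.259 of Visit 1 carriers) compares with counted clearance of 0.216, 0.348 and 0.440, or about 40% to 59% of it.

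**Conclusion.** The omission is real and follows from the text alone: post-infection swabs are excluded from carriage status and acquisition and retained for clearance. The effect on the pooled proportion is small, at most about 0.2 to 0.4 percentage points with 48 primary cases, 5,400 swabbed subjects and 20-50% carriage among cases. It would be larger if cases carry more often, up to 0.9 points if all do. Infections that meet only other efficacy endpoints would add to it, by up to 10 x 0.50 / 5,400 = 0.09 points per ten cases at 50% carriage.

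The case/noncase clearance comparison is the output at risk. Within 90 days nearly all its case clearances would rest on post-infection swabs, although the size of the distortion depends on assumed rates. No primary or secondary analysis is touched. This is a minor correction worth making because it is nearly free.

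**What to change.** In SAP Section 6.3.4, extend the exclusion so that results after a culture-confirmed efficacy endpoint are not used in deriving characterizations, acquisition or clearance. State that for clearance these swabs are treated as missing in both the numerator and the visit denominator. Otherwise cases stay in the denominator with no way to qualify and become non-clearers by construction.

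In Section 8.2.3.4, drop the case/noncase split for clearance, since almost no eligible pre-infection swab pairs would remain in cases. Leave the baseline definition as it is.

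The cost is a short SAP edit, a small change to the derivation program and the loss of one exploratory table.

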### **6.3.5. Immunogenicity**

Titers will be obtained from the OPA assay for CP5 and CP8 and from the cLIA assay for ClfA and MntC. Assay values will be obtained among subjects with adjudication-confirmed *S. aureus*-related SSI and/or BSI and select number of subjects who did not develop adjudication-confirmed *S. aureus* infections at randomization, Visit 2 (both before surgery and after surgery), and Day 90. If 2 or more samples associated with postsurgery are obtained, only the assay results from the latest visit will be eligible for analysis.

Immunogenicity endpoints include the following:

- The proportion of subjects who achieve specific antibody thresholds at each scheduled time point, compiled separately for each antigen/assay. Thresholds are presented in [Table 8](#).

- The proportion of subjects who achieve specific antibody thresholds to all 4 antigens simultaneously at each scheduled time point, limited to CP5/OPA, CP8/OPA, ClfA/cLIA, and MntC/cLIA.
- Geometric mean titer (GMT) at each time point.
- Geometric mean fold rise (GMFR) from Visit 1 to Visit 2 admission.
- Increases of 2-, 4-, 8-, 16-, and 32-fold from Visit 1 to Visit 2 admission.

**Table 8. Threshold Values for Assay/Antigens**

Antigen	Assay Method	Threshold
ClfA	cLIA	≥4-fold rise from Visit 1
MntC	cLIA	≥4-fold rise from Visit 1
CP5	OPA	≥1000
CP8	OPA	≥2000

Abbreviations: ClfA = clumping factor A; cLIA = competitive Luminex immunoassay; CP5 = capsular polysaccharide serotype 5; CP8 = capsular polysaccharide serotype 8; LLOQ = lower limit of quantitation; MntC = manganese transporter C; OPA = opsonophagocytic activity.

Lower limits of quantitation (LLOQs) will be defined in the assay validation report.

The proportions of subjects achieving threshold will be missing for ClfA/cLIA and MntC/cLIA at Visit 1 by definition of its threshold.

Other assays that measure immune response may also be analyzed.

Statistical methodology for immunogenicity is described in [Section 8.1.3.5](#).

#### 6.4. Covariates

No covariates are proposed for the primary and secondary efficacy analyses.

### 7. HANDLING OF MISSING VALUES

Sensitivity analyses for efficacy will be performed if there are suspected PDIs without sufficient microbiological testing to confirm or deny the PDI as microbiologically confirmed *S aureus*. Only the primary and secondary efficacy endpoints will be so analyzed. The suspected PDI cases that meet clinical criteria but lack sufficient microbiological testing will be assigned as confirmed PDI with probability  $P_u$ . The sensitivity analyses will examine a range of  $P_u$  values for each vaccine group.

The ranges of  $P_u$  values are described in [Table 9](#). Simulations are not required for every value. For example, when  $P_u = 0$  in the SA4Ag group and  $P_u = 1$  in the placebo group, then every suspect SA4Ag PDI is considered not to be a PDI and every suspect placebo PDI is considered a confirmed PDI. This is the “best-case” sensitivity analysis for SA4Ag.

The missing-at-random (MAR) analysis uses the observed probabilities ( $P_u$ ) for each vaccine group; SA4Ag's (or placebo's)  $P_u$  will be the number of *S aureus* microbiologically confirmed PDIs divided by the number of PDIs with sufficient nonmissing microbiological testing, limited to subjects in the SA4Ag (placebo) group. The missing-not-at-random (MNAR) analyses use a range of  $P_u$  values that are selected without reference to observed  $P_u$  values.

**Table 9. Range of Probabilities for Sensitivity Analyses on Protocol-Defined Infections that Lack Sufficient Microbiological Confirmation**

Scenario	$P_u = \text{Pr}(\text{PDI is microbiologically confirmed } S \text{ aureus, given SA4Ag vaccination and clinical criteria met})$	$P_u = \text{Pr}(\text{PDI is microbiologically confirmed } S \text{ aureus, given placebo vaccination and clinical criteria met})$	Comments	Simulations
1	0	1	Best -case analysis	N/A
2	1	0	Worst -case analysis	N/A
3	0	0	Observed; missing PDIs not included	N/A
4	1	1	Every suspect PDI is microbiologically confirmed	N/A
5	Observed $P_s^a$	Observed $P_p^b$	MAR	2000
6	0	0.5	MNAR	2000
7	0.5	0	MNAR	2000
8	0.5	0.5	MNAR	2000

a. Observed  $P_s$  = the number of *Staphylococcus aureus* microbiologically confirmed PDIs divided by the number of PDIs with sufficient nonmissing microbiological testing, limited to subjects receiving SA4Ag.

b. Observed  $P_p$  = the number of *S aureus* microbiologically confirmed PDIs divided by the number of PDIs with sufficient nonmissing microbiological testing, limited to subjects receiving placebo.

Abbreviations: MAR = missing at random; MNAR = missing not at random; N/A = not applicable;

PDI = protocol-defined infection; Pr = probability.

If both  $P_u$  values for SA4Ag and placebo are set to zero, then the resulting VE is a complete case analysis. If the  $P_u$  for SA4Ag is 1 and the  $P_u$  for placebo is 0, then the resulting VE is worst-case VE. If the  $P_u$  for SA4Ag is 0 and the  $P_u$  for placebo is 1, then the resulting VE is best-case VE. The distribution of proposed sensitivity analyses is displayed in [Table 10](#).

